4.2.1. Diversity of Study Population

Reasonable attempts will be made to enroll participants with balanced distribution of gender and race to ensure the study population is representative of the patient population that will use abrocitinib in clinical practice.

4.2.2. Choice of Contraception/Barrier Requirements

Human reproductive safety data are not available for abrocitinib, but there is no suspicion of human teratogenicity based on the intended pharmacology of the compound. Therefore, the use of a highly effective method of contraception is required (see [Appendix 4](#)).

CCI

4.3. Justification for Dose

Two hundred mg QD oral doses of abrocitinib will be used in this study as it is the highest dose evaluated in the Phase 3 AD program. Both C_{max} and AUC values of abrocitinib increase in proportion to increases in dose following single administrations of up to 400 mg of abrocitinib. Oral doses of abrocitinib as high as 800 mg (single dose), 400 mg QD and 200 mg BID (up to 10 days) have been found to be safe and well-tolerated. Based on the safety data of abrocitinib and prior clinical experience described above, the 200 mg QD for 10 days is expected to pose little risk to healthy adult participants.

Single oral doses of 100 mg caffeine, 50 mg efavirenz, and 10 mg omeprazole will be used in this study as consistent with the validated Basel cocktail. The probe drugs are expected to be generally safe and well tolerated by healthy participants and have no mutual interactions².

4.4. End of Study Definition

The end of the study is defined as the date of last scheduled procedure shown in the [SoA](#) for the last participant in the study.

A participant is considered to have completed the study if he/she has completed all periods of the study, including the last Follow-up phone call.

5. STUDY POPULATION

This study can fulfill its objectives only if appropriate participants are enrolled. The following eligibility criteria are designed to select participants for whom participation in the study is considered appropriate. All relevant medical and nonmedical conditions should be taken into consideration when deciding whether a particular participant is suitable for this protocol.

Prospective approval of protocol deviations to recruitment and enrollment criteria, also known as protocol waivers or exemptions, is not permitted.

5.1. Inclusion Criteria

Participants are eligible to be included in the study only if all of the following criteria apply:

Age and Sex:

1. Participants must be ≥ 18 years of age at the time of signing the ICD.
 - Refer to [Appendix 4](#) for reproductive criteria for male ([Section 10.4.1](#)) and female ([Section 10.4.2](#)) participants.

Type of Participant and Disease Characteristics:

2. Male and female participants who are healthy as determined by medical evaluation including a detailed medical history, complete physical examination, laboratory tests, and cardiovascular tests.
3. Participants who are willing and able to comply with all scheduled visits, treatment plan, laboratory tests, lifestyle considerations, and other study procedures.

Weight:

4. BMI of 17.5 to 32 kg/m²; and a total body weight >50 kg (110 lb).

Informed Consent:

5. Capable of giving signed informed consent as described in [Appendix 1](#), which includes compliance with the requirements and restrictions listed in the ICD and in this protocol.

5.2. Exclusion Criteria

Participants are excluded from the study if any of the following criteria apply:

Medical Conditions:

1. Evidence or history of clinically significant hematological, renal, endocrine, pulmonary, gastrointestinal, cardiovascular, hepatic, psychiatric, neurological, or allergic disease (including drug allergies, but excluding untreated, asymptomatic, seasonal allergies at the time of dosing).
2. Any condition possibly affecting drug absorption (eg, gastrectomy, cholecystectomy).
3. Participants with moderate to severe GERD symptoms (ie, heartburn and/or regurgitation) during the last 6 months.
4. History of HIV infection, hepatitis B, or hepatitis C; positive testing for HIV, HBsAg, or HCVAb. Hepatitis B vaccination is allowed.
5. Other medical or psychiatric condition including recent (within the past year) or active suicidal ideation/behavior or laboratory abnormality that may increase the risk of study participation or, in the investigator's judgment, make the participant inappropriate for the study.
6. Evidence or history of clinically significant dermatological condition (eg, AD or psoriasis) or visible rash present during physical examination.
7. History of TB (active or latent) or inadequately treated TB infection. Positive QuantiFERON® – TB Gold test.
8. Any history of chronic infections, any history of recurrent infections, any history of latent infections, or any acute infection within 2 weeks of baseline (Day -1).
9. History of disseminated herpes zoster, or disseminated herpes simplex, or recurrent localized dermatomal herpes zoster.
10. Have any malignancies or have a history of malignancies with the exception of adequately treated or excised nonmetastatic basal cell or squamous cell cancer of the skin, or cervical carcinoma *in situ*.
11. History of hypersensitivity, intolerance, or allergic reaction associated to prior exposure to caffeine, omeprazole, efavirenz, and abrocitinib or any of their excipients.

12. Any psychiatric condition including recent or active suicidal ideation or behavior that meets any of the following criteria:

- Suicidal ideation associated with actual intent and a method or plan in the past year: “Yes” answers on items 4 or 5 of the C-SSRS ([Section 8.2.7](#)).
- For participants who had previous history of suicidal behaviors in the past >1 year to 10 years: “Yes” answer (for events that occurred in the past 10 years) to any of the suicidal behavior items of the C-SSRS or any lifetime history of serious or recurrent suicidal behavior, a risk assessment must be performed, and documented, by a qualified MHP to assess whether it is safe for the participant to participate in the trial.
- The presence of any current major psychiatric disorder that is not explicitly permitted in the inclusion/exclusion criteria.

NOTE: For any participant who has significant depression or any suicidal behavior, the participant will not be randomized and should be referred for appropriate evaluation and treatment.

13. Participants, who according to the product label for efavirenz, would be at increased risk if dosed with efavirenz (ie, including but not limited to patients with severe hepatic impairment [Child Pugh Class C]).

14. Participants, who according to the product label for efavirenz, with a history of seizures.

Prior/Concomitant Therapy:

15. Use of prescription or nonprescription drugs and dietary and herbal supplements within 7 days or 5 half-lives (whichever is longer) prior to the first dose of study intervention. (Refer to [Section 6.8](#) for additional details).

16. Systemic therapy with any of the medications that are moderate or strong CYP1A2, CYP2B6, or CYP2C19 inhibitors within 28 days or 5 half-lives (whichever is longer) or moderate or strong CYP1A2, CYP2B6, or CYP2C19 inducers within 28 days or 5 half-lives (whichever is longer) prior to the first dose.

17. Herbal supplement, hormonal contraceptives and HRT must be discontinued at least 28 days prior to the first dose of investigational product; Depo-Provera® must be discontinued at least 6 months prior to dosing of investigational product.

18. Participants who are vaccinated with vaccines that have live components (or live attenuated vaccines) within the 6 weeks prior to the first dose of abrocitinib or who are expected to be vaccinated during treatment or during the 6 weeks following discontinuation of abrocitinib.

NOTE regarding COVID vaccines with authorization or approval for emergency use:

There is no requirement for washout of COVID vaccines prior to the first dose of abrocitinib if the vaccine is not live attenuated (eg, mRNA, utilizing a viral vector, inactivated virus).

There is no protocol-specified requirement for the interruption of abrocitinib dosing prior to or after vaccination if the COVID vaccine is not live attenuated.

Prior/Concurrent Clinical Study Experience:

19. Previous administration with an investigational drug within 30 days (or as determined by the local requirement) or 5 half-lives preceding the first dose of study intervention used in this study (whichever is longer).

Diagnostic Assessments:

20. A positive urine drug test.
21. Screening supine BP ≥ 140 mm Hg (systolic) or ≥ 90 mm Hg (diastolic), following at least 5 minutes of supine rest. If BP is ≥ 140 mm Hg (systolic) or ≥ 90 mm Hg (diastolic), the BP should be repeated 2 more times and the average of the 3 BP values should be used to determine the participant's eligibility.
22. Baseline standard 12-lead ECG that demonstrates clinically relevant abnormalities that may affect participant safety or interpretation of study results (eg, baseline QTcF interval >450 msec, complete LBBB, signs of an acute or indeterminate-age myocardial infarction, ST-T interval changes suggestive of myocardial ischemia, second- or third-degree AV block, or serious bradyarrhythmias or tachyarrhythmias). If the baseline uncorrected QT interval is >450 msec, this interval should be rate-corrected using the Fridericia method and the resulting QTcF should be used for decision making and reporting. If QTcF exceeds 450 msec, or QRS exceeds 120 msec, the ECG should be repeated 2 more times and the average of the 3 QTcF or QRS values should be used to determine the participant's eligibility. Computer-interpreted ECGs should be overread by a physician experienced in reading ECGs before excluding a participant.

23. Participants with **ANY** of the following abnormalities in clinical laboratory tests at screening, as assessed by the study-specific laboratory and confirmed by a single repeat test, if deemed necessary:
 - AST **or** ALT level $\geq 1.5 \times$ ULN;
 - TBili level $\geq 1.5 \times$ ULN; participants with a history of Gilbert's syndrome may have direct bilirubin measured and would be eligible for this study provided the direct bilirubin level is $\leq 1.5 \times$ ULN.
 - eGFR < 60 mL/min/1.73 m² (see [Appendix 2](#) for CKD-EPI formula).
 - In the opinion of the investigator or Pfizer (or designee), have any clinically significant laboratory abnormality that could affect interpretation of study data or the participant's participation in the study.
24. Participants with abnormal complete blood count test results (eg, hemoglobin, platelets, WBCs- including lymphocytes, neutrophils) as assessed by the study specific laboratory, and confirmed by a single repeat test, if deemed necessary.

Other Exclusions:

25. History of alcohol abuse or binge drinking and/or any other illicit drug use or dependence within 6 months of Screening. Binge drinking is defined as a pattern of 5 (male) and 4 (female) or more alcoholic drinks in about 2 hours. As a general rule, alcohol intake should not exceed 14 units per week (1 unit = 8 ounces (240 mL) beer, 1 ounce (30 mL) of 40% spirit or 3 ounces (90 mL) of wine).
26. Pregnant female participants; breastfeeding female participants; female participants of childbearing potential who are unwilling or unable to use 1 highly effective method of contraception as outlined in this protocol (see [Appendix 4, Section 10.4](#)) for the duration of the study and for at least 28 days after the last dose of study intervention.
27. Participants who routinely consumed more than five 8-ounce cups of coffee (or caffeine equivalent) or greater than 6 servings (1 serving is approximately equivalent to 125 mg of caffeine) of tea, Cola or other caffeinated beverage per day.
28. Consumption of chocolate and chocolate-containing products (eg, hot chocolate, ice cream, cookies, etc) within 48 hours prior to the first dose and during the study.
29. Smokers and/or participants who used nicotine based products within 3 months prior to the first dose of the investigational product.
30. Consumption of charcoal-broiled beef within 7 days prior to the first dose as it is known to induce CYP1A2 enzyme.

31. Consumption of cruciferous vegetables (eg, cauliflower, broccoli, Brussel sprouts, and cabbage) within 7 days prior to the first dose as cruciferous vegetables are known to increase CYP1A2 activity.
32. Blood donation (excluding plasma donations) of approximately 1 pint (500 mL) or more within 60 days prior to dosing.
33. Unwilling or unable to comply with the criteria in the Lifestyle Considerations section of this protocol.
34. Investigator site staff or Pfizer employees directly involved in the conduct of the study, site staff otherwise supervised by the investigator, and their respective family members.

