4. STUDY DESIGN

4.1. Overall Design

This is a Phase 1, open-label, multiple dose, single fixed-sequence, 2-period study to evaluate the effect of abrocitinib on the PK of caffeine, efavirenz and omeprazole in healthy adult participants. A total of approximately 13 healthy male and/or female participants will be enrolled in the study to obtain at least 12 evaluable participants who complete the study. Participants who withdraw from the study or are considered non-evaluable may be replaced at the discretion of the sponsor.

Participants will be screened within 28 days of the first dose of study intervention. Participants will have a phone contact 3 days prior to Day 1 dosing (Day -3) in Period 1 as a reminder to abstain from caffeine-containing products. Participants will be admitted to the CRU at least 24 hrs prior to Day 1 dosing (Day -1) in Period 1. Participants will remain in the CRU for a total of 15 days and 14 nights.

In Period 1, all the participants will receive single doses of probe drugs, including caffeine 100 mg, efavirenz 50 mg and omeprazole 10 mg, together on Day 1. The Day 1 of Period 2 begins on the fourth day following the start of Period 1. The predose and up to 24 hours post

dose PK samples will be analyzed for caffeine, efavirenz, and omeprazole; while the 48 and 72 hours post dose PK samples will be analyzed for efavirenz PK only. After 3 days of PK sampling in Period 1, Period 2 will immediately follow with no washout.

In Period 2, participants will receive abrocitinib 200 mg QD on Day 1-10. On Period 2 Day 2, participants will receive single dose of omeprazole 10 mg alone within approximately 5 minutes after administration of a 200 mg dose of abrocitinib in the morning. PK samples for omeprazole concentration measurement will only be collected from predose and up to 8 hours post dose. Participants will receive single doses of the probe drugs (caffeine 100 mg, efavirenz 50 mg and omeprazole 10 mg together) again on Day 8, and omeprazole 10 mg alone on Day 2, within approximately 5 minutes after administration of abrocitinib 200 mg on the morning of the respective day. The predose and up to 24 hours post dose PK samples will be analyzed for caffeine, efavirenz, and omeprazole; while the 48 and 72 hours post dose PK samples will be analyzed for efavirenz PK only.

Participants will have a telephone contact between 28-35 calendar days after the last administration of the investigational product.

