5.3.1. Meals and Dietary Restrictions

- Participants must abstain from all food and drink (except water) at least 4 hours prior to any safety laboratory evaluations and 10 hours prior to the collection of the predose PK sample.
- Water is permitted until 1 hour prior to study intervention administration. Water may be consumed without restriction beginning 1 hour after dosing. Noncaffeinated drinks (except grapefruit or grapefruit-related citrus fruit juices—see below) may be consumed with meals and the evening snack.
- Lunch will be provided approximately 4 hours after dosing.
- Dinner will be provided approximately 9 to 10 hours after dosing.
- An evening snack may be permitted.
- Participants will refrain from consuming red wine, grapefruit, or grapefruit-related citrus fruits (eg, Seville oranges, pomelos, fruit juices) from 7 days prior to the first dose of study intervention until collection of the final PK blood sample.
- While participants are confined, their total daily nutritional composition should be approximately 55% carbohydrate, 30% fat, and 15% protein. The daily caloric intake per participant should not exceed approximately 3200 kcal.

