5.3.2. Caffeine, Alcohol, and Tobacco

- Participants will abstain from caffeine-containing products for 48 hours prior to the start of dosing until collection of the final PK sample of each study period.
 - Caffeine-containing products including but not limited to coffee, tea, Cola or other caffeinated beverage (eg, energy drinks), chocolate and chocolate-containing products (eg, hot chocolate, ice cream, cookies, etc), guarana.
- Participants will abstain from alcohol for 24 hours prior (or as specified above for red wine) to admission to the CRU and continue abstaining from alcohol until collection of the final PK sample of each study period. Participants may undergo an alcohol breath test or blood alcohol test at the discretion of the investigator.
- Participants will abstain from the use of tobacco- or nicotine- containing products for 3 months prior to the start of study intervention in Period 1 and continue abstaining from tobacco- or nicotine-containing products until collection of the final PK sample of Period 2.

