9.3.1.2. Derivation of Pharmacokinetic Parameters

PK parameters will be derived from the plasma concentration time profiles as shown in Table 3.

Table 3. Plasma Pharmacokinetic Parameter Definitions

Parameter	Definition	Method of Determination
AUC _{last}	area under the concentration-time curve from time 0 to time of the last measureable concentration	Linear/Log trapezoidal rule
AUC _{inf}	area under the concentration-time curve from time 0 to infinity	AUC _{last} + (C _{last} [*] /k _{el}), where C _{last} [*] is the predicted plasma concentration at the last quantifiable time point estimated from the loglinear regression analysis, and k _{el} is the terminal phase rate constant calculated by a linear regression through at least 3 data points in the terminal phase of the loglinear concentration time curve
CC		
CC		
CCI		
CCI		
C		
C		
I		

Natural log-transformed parameters (AUC_{inf}, AUC_{last} CCI) will be analyzed using a mixed effect model with treatment as a fixed effect and subject as a random effect. Estimates of the adjusted mean differences (Test-Reference) and corresponding 90% CIs will be obtained from the model. The adjusted mean differences and 90% CIs for the differences will be exponentiated to provide estimates of the ratio of adjusted geometric means (Test/Reference) and 90% CI for the ratios. The Test and Reference treatments to estimate the treatment difference for each of the study objectives are as follows:

- Objective 1: caffeine 100 mg (Period 1, Day 1) will be the Reference treatment; abrocitinib 200 mg + caffeine 100 mg (Period 2, Day 8) will be the Test treatment.
- Objective 2: efavirenz 50 mg (Period 1, Day 1) will be the Reference treatment; abrocitinib 200 mg + efavirenz 50 mg (Period 2, Day 8) will be the Test treatment.
- Objective 3: omeprazole 10 mg (Period 1, Day 1) will be the Reference treatment; abrocitinib 200 mg + omeprazole 10 mg (Period 2, Day 8) will be the Test treatment.

Residuals from the model will be examined for normality and the presence of outliers via visual inspection of plots of residuals vs predicted values and normal probability plots of residuals but these will not be included in the CSR. If there are major deviations from normality or outliers, then the effect of these on the conclusions will be investigated through alternative transformations and/or analyses excluding outliers. Justification for any alternative to the planned analysis will be given in the report of the study.

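### The bar on foods the protocol says raise CYP1A2 activity ends at the first dose, leaving the Test caffeine dose unprotected

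*Protocol*

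**What the plan says.** Two exclusion criteria in Protocol Section 5.2 deal with foods that affect CYP1A2. Item 30 is "Consumption of charcoal-broiled beef within 7 days prior to the first dose as it is known to induce CYP1A2 enzyme". Item 31 is "Consumption of cruciferous vegetables (eg, cauliflower, broccoli, Brussel sprouts, and cabbage) within 7 days prior to the first dose", with increased CYP1A2 activity again given as the reason. Both windows close at the first dose.

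Other restrictions are expressly carried into the study:

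- Red wine, grapefruit and related citrus (Section 5.3.1) are barred "from 7 days prior to the first dose of study intervention until collection of the final PK blood sample".
- Section 5.3.2 has participants "continue abstaining from tobacco- or nicotine-containing products until collection of the final PK sample of Period 2".
- Item 28 of Section 5.2 bars chocolate both before the first dose and while the study runs.

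Section 4.1 states: "Participants will remain in the CRU for a total of 15 days and 14 nights". For that stay, Section 5.3.1 sets meal times, a calorie cap and a macronutrient split ("While participants are confined, their total daily nutritional composition should be approximately 55% carbohydrate, 30% fat, and 15% protein"). It names neither charcoal-broiled beef nor cruciferous vegetables. Item 33 excludes anyone "Unwilling or unable to comply with the criteria in the Lifestyle Considerations section of this protocol", but it can enforce only what that section contains.

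For caffeine, Protocol Section 9.3.1.2 and SAP Section 8.2 take Period 1 Day 1 as Reference and Period 2 Day 8 with abrocitinib as Test.

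**The concern.** The protocol treats these foods as able to change the activity of the enzyme that caffeine is there to measure, yet it controls them before only one of the two caffeine doses being compared. Each participant is their own control and all follow the same order. A change in diet between the two doses is therefore indistinguishable from the effect of abrocitinib.

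Direction matters. Sections 2.2.2 and 4.2 describe abrocitinib as a weak CYP1A2 inducer, and Section 4.2 places the Test dose on Day 8 because induction takes several days to develop. Dietary induction arising over those same days would lower caffeine AUC, as abrocitinib induction would. The study could then report a CYP1A2 effect, or a larger one, that came partly from the menu. Because all participants eat the unit's meals, such a shift could affect the whole group at once, and averaging over participants would not remove it.

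The point concerns caffeine only. The documents do not link these foods to CYP2B6 or CYP2C19.

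**Working it through.** **Timing.** Section 4.1 starts Period 2 on the fourth day, so Period 2 Day 1 is study day 4 and Period 2 Day 8 is study day 4 + 7 = 11. That is 11 − 1 = 10 days after the first dose.

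| Caffeine dose | Study day | The 7 days before it | Foods barred in those days? |
|---|---|---|---|
| Reference, Period 1 Day 1 | 1 | before the first dose | Yes (items 30–31) |
| Test, Period 2 Day 8 | 11 | study days 4–10 | No |

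Reading the first dose as the first abrocitinib dose does not close the gap. That dose is on study day 4, exactly 7 days before Test, so days 4–10 are still uncovered.

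**The plan's own precision figure.** Inputs from Section 9.5 are n = 12, within-participant SD of ln AUCinf for caffeine 0.13, a 90% CI and 80% coverage probability.

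- Half-width without the coverage factor: t(0.95, 11) × 0.13 × √(2/12) = 0.0953.
- Coverage factor: √(χ²(0.80, 11)/11) = 1.1533.
- Product: 0.0953 × 1.1533 = 0.1099, as stated.
- At an estimated effect of 100%, exp(±0.1099) gives 89.59% to 111.62%, which matches Table 4.

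**Break-even sizes.** The documents give no size for the food effect, so the useful question is how large it would have to be to matter. Assume that the AUC ratio is the reciprocal of the clearance ratio, that abrocitinib has no true effect, and that the dietary shift is common to all participants, present at Test and absent at Reference. A shift equal to a fraction k of the half-width then needs a clearance rise of exp(k × 0.1099) − 1 and gives an apparent ratio of exp(−k × 0.1099).

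| k | Rise in caffeine clearance at Test | Apparent Test/Reference ratio |
|---|---|---|
| 0.25 | 2.8% | 0.973 |
| 0.50 | 5.6% | 0.947 |
| 1.00 | 11.6% | 0.896 |

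The last ratio is the lower limit in Table 4 for an estimated effect of 100% (89.59). Caffeine has the narrowest planned interval of the three probes (0.1099, against 0.2029 for efavirenz and 0.2114 for omeprazole), so a given shift counts for most here. These are thresholds, not predictions.

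**The case against.** The strongest reply is that no harm is shown. Participants are confined and their meals are provided, so bias requires the unit to serve foods that its own protocol identifies as CYP1A2 inducers. It may well not do so, and a protocol need not contain a menu. The break-even figures were worked back from the half-width and say nothing about likely intake or effect. All of this stands, and it is why the size is left open. It does not remove the gap: grapefruit is restricted on study despite the same confinement, so the protocol did not treat confinement as sufficient there.

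No prespecified conclusion depends on the result either. Protocol Section 9.1 and SAP Section 4 set no hypotheses or decision rules. That is correct, but the estimate and its interval are the study's product, and a biased ratio is a fault in an estimation study too.

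The likely error is an overstated induction signal, not false reassurance. Section 2.2.2 reports no significant competitive CYP inhibition and lists time-dependent inhibition only for CYP3A, CYP2C19 and CYP2D6, so there is little reason to fear masked CYP1A2 inhibition. This lowers the seriousness but leaves the bias.

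It is also fair to say that the inability to separate diet from drug belongs to the fixed-sequence design and is not a fault of the model (treatment fixed, subject random). That is the reason to control diet in conduct, since no analysis can do so afterwards.

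Finally, a bar running to the last PK sample extends about 48 hours past the last caffeine measurement: caffeine is assayed to 24 hours, and the 48- and 72-hour samples are for efavirenz only. This is true and harmless.

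**Conclusion.** The gap is real and worth closing. The restriction stops too early for its stated purpose: the Reference caffeine dose has a 7-day protected window and the Test dose has none. If these foods are served between the two doses, any induction they cause enters the caffeine ratio in full and cannot be recovered in analysis.

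Whether any bias arises depends on a menu the documents do not specify, and its size on an effect they do not quantify; it may be zero. A common rise in caffeine clearance of 11.6% would equal the whole planned half-width, under the assumptions set out with the table. The sample size and precision figures in Section 9.5 reproduce and are unaffected, as are the efavirenz and omeprazole comparisons.

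**What to change.** Add one bullet to Protocol Section 5.3.1 barring charcoal-broiled beef and cruciferous vegetables over the same span as grapefruit, that is, "from 7 days prior to the first dose of study intervention until collection of the final PK blood sample", and stating that CRU menus omit both foods in both periods. Keep items 30 and 31 as entry criteria. Item 33 already ties eligibility to the Lifestyle Considerations section, so no other criterion needs to change.

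The cost is a short text change and a menu instruction to the unit, with no added visits, samples or participants. If made after approval, Section 10.1.1 may require IRB/EC approval before implementation, and health authority approval too if the amendment is classed as substantial.
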